2.2 EFFICACY ENDPOINTS

Progression-free survival (PFS)

PFS is defined as the interval from Cycle 1/Day 1 to the earlier of the first documentation of definitive disease progression or death from any cause. Definitive disease progression based on standard criteria (Hallek et al. 2008) and occurring for any reason (i.e., increasing lymphadenopathy, organomegaly or bone marrow involvement; decreasing platelet count, hemoglobin, or neutrophil count; or worsening of disease-related symptoms) other than lymphocytosis.

Time to treatment failure (TTF)

TTF is defined as a composite endpoint measuring time from Cycle 1/Day 1 to discontinuation of treatment for any reason, including disease progression, treatment toxicity, and death.

Overall response rate (ORR)

ORR is defined as sum of CR and PR rates.

Duration of response (DOR)

DOR is defined as the interval from the first documentation of CR or PR to the earlier of the first documentation of definitive disease progression or death from any cause.

3 ELIGIBILITY CRITERIA

Patients must meet all of the following inclusion criteria and none of the exclusion criteria to be eligible for participation in this study.

3.1 INCLUSION CRITERIA

Patients must meet all of the following inclusion criteria to be eligible for participation in this study:

- 1. Confirmed diagnosis of CLL as per the iwCLL (Hallek 2008) criteria
- CLL warranting therapy as per investigator discretion.
- 3. Patients must be off prior BTK and/or PI3K-delta inhibitor for at least 14 days following discontinuation without documented disease progression. This is to ensure the reason for discontinuation was intolerance, not disease progression as listed below, # 4 7. Patients may sign consent during the washout period.
- 4. For ibrutinib/BTK patients who experience related hematologic and non-hematologic toxicities and discontinue therapy (see bullet 7). Non-hematologic toxicities are limited to: Atrial fibrillation, Hypertension, Bleeding, Arthralgia, Rash, Diarrhea, Infection, Pneumonitis.
- For idelalisib/duvelisib patients who experience related hematologic and non-hematologic toxicities and discontinue therapy (see bullet 7). Non-hematologic toxicities are limited to: Pneumonitis, Transaminitis, Rash, Colitis, and Infection.
- 6. Other grade ≥ 2 non-hematologic toxicities not listed in 4 or 5, despite dose interruption and/or reduction, and defined by the treating investigator as "intolerant", will be evaluated individually by the study chair as part of eligibility criteria as part of the screening process.
- Prior therapy with a BTK inhibitor (ibrutinib, ACP-196, other) or a PI3K-delta inhibitor (idelalisib, duvelisib, other) which was discontinued, due to intolerance, within 12 months of the time of treatment initiation with umbralisib (Cycle 1/Day 1).
 - a. Intolerance defined as unacceptable toxicity where in the opinion of the investigator, treatment should be discontinued in spite of optimal supportive care as a result of one of the following:
 - i. ≥ 2 Grade ≥ 2 non-hematological toxicities (see list above, #4-6) as a cause of discontinuation, and/or;
 - ii. ≥ 1 Grade ≥ 3 non-hematological toxicity (see list above, #4-6), and/or;
 - iii. ≥ 1 Grade 3 neutropenia with infection or fever, and/or;
 - iv. Grade 4 hematological toxicities, AND the toxicities persistent to the point that the investigator chose to discontinue therapy due to toxicity / not progression.
 - v. Toxicity must resolve to ≤ grade 1 prior to umbralisib dosing.
- 8. Adequate organ system function, defined as follows:
 - Absolute neutrophil count (ANC) ≥ 1,000 / platelet count ≥ 30,000. Growth factors are permitted at any time during the study.
 - b. Total bilirubin ≤1.5 times the upper limit of normal (ULN)
 - c. Alanine aminotransferase (ALT) and aspartate aminotransferase (AST) ≤2.5 x ULN if no liver involvement or ≤5 x the ULN if known liver involvement
 - d. Calculated creatinine clearance >30 mL/min (as calculated by the Cockcroft-Gault or MDRD formula, 24- hour urine Cr clearance also acceptable)
- ECOG performance status ≤ 2
- 10. Male or female ≥ 18 years of age
- 11. Ability to swallow and retain oral medication

TGR-1202-201-CLL

- 12. Female patients who are not of child-bearing potential and female patients of child-bearing potential who have a negative serum pregnancy test within 3 days prior to Cycle 1, Day 1.
- Willingness and ability to comply with trial and follow-up procedures, and give written informed consent.

3.2 EXCLUSION CRITERIA

Patients who meet any of the following exclusion criteria are not to be enrolled to this study:

[figure not shown]
- 1. Patients receiving a BTK or PI3K-delta inhibitor within 14 days of Cycle 1/Day 1.
 - a. Corticosteroid therapy started at least 7 days prior to study entry (prednisone ≤10 mg daily or equivalent) is allowed as clinically warranted. Topical or inhaled corticosteroids are permitted.
- 2. Disease progression as defined by IWCLL (Hallek 2008) criteria as the indication for discontinuation on or within 14 days with a prior BTK or PI3K-delta inhibitor.
- 3. Prior treatment with umbralisib.
- 4. Prior autologous stem cell transplant within 3 months. Prior allogeneic hematologic stem cell transplant within 1 year and excluded if there is active graft versus host disease.
- 5. Anaphylaxis to prior kinase inhibitor therapy.
- 6. Evidence of chronic active Hepatitis B (HBV, not including patients with prior hepatitis B vaccination; or positive serum Hepatitis B antibody) or chronic active Hepatitis C infection (HCV), cytomegalovirus (CMV), or known history of HIV. If HBc antibody, HCV antibody or CMV is positive the subject must be evaluated for the presence of HBV, HCV, or CMV by DNA (PCR) See Appendix D.
- Known histological transformation from CLL to an aggressive lymphoma (i.e. Richter's transformation / Hodgkin Lymphoma).
- Evidence of ongoing systemic bacterial, fungal or viral infection, except localized fungal infection of skin/nails.
- Any severe and/or uncontrolled medical conditions or other conditions that could affect their participation in the study such as:
 - Symptomatic, or history of documented congestive heart failure (NY Heart Association functional classification III-IV) – See Appendix C
 - b. Myocardial infarction within 6 months of enrollment
 - c. QTcF >470 msec
 - d. Angina not well-controlled by medication
 - Poorly controlled or clinically significant atherosclerotic vascular disease including cerebrovascular accident (CVA), transient ischemic attack (TIA), angioplasty, cardiac/vascular stenting within 6 months of enrollment.
- 10. Malignancy within 3 years of study enrollment except for adequately treated basal, squamous cell carcinoma or non-melanomatous skin cancer, carcinoma in situ of the cervix, superficial bladder cancer not treated with intravesical chemotherapy or BCG within 6 months, localized prostate cancer and PSA <1.0 mg/dL on 2 consecutive measurements at least 3 months apart with the most recent one being within 4 weeks of study entry.

- 11. Women who are pregnant or lactating.

TGR-1202-201-CLL

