5 STUDY ASSESSMENTS AND TREATMENT SCHEDULE

Error! Reference source not found. The Table below lists study assessments that should be performed at each study visit.

STUDY ASSESSMENTS AND TREATMENT SCHEDULE

All cycles are 28 days	Screening	Cycle 1 ¹		Cycles 2 - 6 ²	> Cycle 6 ³	ЕОТ	30 day	
	D-30 to D0	D1	D8	D15	D1	Every 3 cycles	EOI	F/U
Informed Consent	X							
Medical History	X							
ECOG Performance Status	X	X			X	X	X	
Physical Examination/Vitals (Weight, Temp, BP, HR, RR)	X	X	X	X	X	x	X	
EKG (QtcF)	X							
Serology HCV, HBV, CMV	X4							
CMV surveillance					C3&6	X5		
Hematology	X	X	X	X	X	X	X	
Chemistry	X	X	X	X	X	X	X	
CT Imaging (neck, chest, abdomen, pelvis)	X ⁶	During Cycles 3, 6, 9, 12 and at least every 6 cycles for 24 cycles, then every 12 cycles thereafter or more frequent if warranted (+/- 14 days)			X ⁷			
Serum Pregnancy Test	X8		1					
Urine Pregnancy Test ⁹					X	X		
Collect Buccal Swab for Somatic DNA ¹⁰	Х							
Correlative Labs (PB) ¹⁰	Х				Cycle 2		Disease progression	
Peripheral Blood ¹¹	X							
Umbralisib	Daily Days 1 - 28							
Bone Marrow Biopsy ¹²	X							
AE Assessment		X	X	X	X	X	X	X13
Con med Assessment		X	X	X	X	X	X	

¹ Physical Exam, Vitals, ECOG, treatment administration, AEs, conmeds, hematology, serum chemistry visit days have +/- 1 day window. Assessments must be done within the specified window, but only prior to initiation of next cycle.

² Physical Exam, Vital Signs, ECOG PS, treatment administration, AEs, conmeds, hematology, serum chemistry visit days have +/- 3 day window in Cycles 2 - 6. Assessments must be done prior to treatment administration. Assessments must be done within the specified window, but only prior to initiation of next cycle.

³ Physical Exam, Vital Signs, ECOG PS, treatment administration, AEs, conmeds, hematology, serum chemistry visit days have +/- 7 day window for Cycles > 6. Assessments must be done prior to treatment administration. Assessments must be done within the specified window, but only prior to initiation of next cycle.
4 Serum virology to include HBsAg, HBsAb, HBc antibody, HCV antibody and CMV. If HBc antibody, HCV antibody or CMV is positive, subjects must be evaluated for the presence of active HBV, HCV or CMV by DNA (PCR).

⁵ Every 3 months CMV screening by PCR. CMV surveillance will discontinue 30 days after last dose of umbralisib, or as otherwise clinically indicated per investigator discretion.

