5.1.1 LOCAL LABORATORY ASSESSMENTS

Hematologic profile and serum chemistry to include (within 30 days of Cycle 1/Day 1):

Hematologic Profile						
Hematocrit	Neutrophils	Platelet count				
Hemoglobin	Lymphocytes	Absolute lymphocyte count				
Erythrocyte count	Monocytes	Leukocyte count				
Basophils	Eosinophils	Absolute neutrophil count				
Serum Chemistry						
Albumin	Creatinine	SGOT [AST]				
Alkaline phosphatase	Glucose	SGPT [ALT]				
Bicarbonate/CO2	LDH	Sodium				
BUN	Magnesium	Total bilirubin				
Calcium	Phosphorus	Total protein				
Chloride	Potassium	Uric acid				

Hematologic and Serum Chemistry windows as follows:

- Cycle 1: 1 day window
- Cycles 2 6: 3 day window
- > Cycle 6: 7 day window
- Serum β-HCG test.
- Serum Virology to include HBsAG, HbSAb, HBc antibody, HCV antibody, and CMV. If HBc antibody, HCV antibody or CMV are positive the subject must be evaluated for the presence of active HBV, HCV or CMV by DNA (PCR) - See Appendix D.
- 4. Baseline bone marrow aspirate/biopsy (if indicated or warranted).
- CMV surveillance every 3 months by PCR. CMV surveillance will discontinue 30 days after last dose of umbralisib, or as otherwise clinically indicated per investigator discretion.

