17 APPENDIX C - NYHA CLASSIFICATIONS

New York Heart Association (NYHA) Classifications

Class	Functional Capacity	Objective Assessment	
I	Patients with cardiac disease but without resulting limitations of physical activity. Ordinary physical activity does not cause undue fatigue, palpitation, dyspnea, or anginal pain.	cardiovascular disease.	
II	Patients with cardiac disease resulting in slight limitation of physical activity. They are comfortable at rest. Ordinary physical activity results in fatigue, palpitation, dyspnea, or anginal pain.	minimal cardiovascular	
III	Patients with cardiac disease resulting in marked limitation of physical activity. They are comfortable at rest. Less than ordinary activity causes fatigue, palpitation, dyspnea, or anginal pain.	moderately severe	
IV	Patients with cardiac disease resulting in inability to carry on any physical activity without discomfort. Symptoms of heart failure or the anginal syndrome may be present even at rest. If any physical activity is undertaken, discomfort is increased.	Objective evidence of severe cardiovascular disease.	

Source: The Criteria Committee of New York Heart Association. Nomenclature and Criteria for Diagnosis of Diseases of the Heart and Great Vessels. 9th Ed. Boston, MA: Little, Brown & Co; 1994:253-256.

Interpretation of Hepatitis B Serologic Test Results

Hepatitis B scrologic testing involves measurement of several hepatitis B virus (HBV)-specific antigens and antibodies. Different serologic "markers" or combinations of markers are used to identify different phases of HBV infection and to determine whether a patient has acute or chronic HBV infection, is immune to HBV as a result of prior infection or vaccination, or is susceptible to infection.

HBsAg anti-HBc anti-HBs	negative negative negative	Susceptible
HBsAg anti-HBc anti-HBs	negative positive positive	Immune due to natural infection
HBsAg anti-HBc anti-HBs	negative negative positive	Immune due to hepatitis B vaccination
HBsAg anti-HBc IgM anti-HBc anti-HBs	positive positive positive negative	Acutely infected
HBsAg anti-HBc IgM anti-HBc anti-HBs	positive positive negative negative	Chronically infected
HBsAg anti-HBc anti-HBs	negative positive negative	Interpretation unclear; four possibilities; 1. Resolved infection (most common) 2. False-positive anti-HBc, thus susceptible 3. "Low level" chronic infection 4. Resolving acute infection

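### A positive HCV antibody must be followed up by a DNA PCR, but hepatitis C is an RNA virus, so this mandatory eligibility test names the wrong target in four places

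*Combined protocol and SAP*

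**What the plan says.** Section 3.2, exclusion 6, lists among its excluded conditions "chronic active Hepatitis C infection (HCV), cytomegalovirus (CMV), or known history of HIV". It then sets a reflex test: if HBc antibody, HCV antibody or CMV is positive, the subject "must be evaluated for the presence of HBV, HCV, or CMV by DNA (PCR", with a pointer to Appendix D. The synopsis repeats the criterion.

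Footnote 4 of the Section 5 schedule gives the same rule with the aim made explicit: "subjects must be evaluated for the presence of active HBV, HCV or CMV by DNA (PCR". Section 5.1.1, on local laboratory assessments, agrees: "the subject must be evaluated for the presence of active HBV, HCV or CMV by DNA (PCR".

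Appendix D carries the title "Interpretation of Hepatitis B Serologic Test Results". A separate item in Section 3.2 excludes subjects with "Evidence of ongoing systemic bacterial, fungal or viral infection, except localized fungal infection of skin/nails" and names no assay.

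**The concern.** The reflex test is mandatory, and it is the only scheduled test of whether HCV is active in an antibody-positive subject. One phrase, DNA PCR, is applied to three viruses. It suits HBV and CMV. It does not suit HCV, whose genome is RNA: a PCR run on a DNA template without reverse transcription has nothing to amplify, so a negative result would say nothing about active infection.

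At stake is whether the screening step does its job for an HCV-antibody-positive subject. The site must either order what is written and learn nothing, or order the appropriate assay and depart from the text of an eligibility criterion. Neither is a good position for a mandatory test used at up to 20 centers (Section 4.3).

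**Working it through.** No arithmetic applies, and the plan has no figure to reproduce. The check is a comparison of the places that state or could correct the rule. The genome types are general virology and are not stated in the documents.

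1. **The four statements of the rule.**

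| Place | Viruses covered | Target named | Aim stated |
|---|---|---|---|
| Synopsis, exclusion 6 | HBV, HCV, CMV | DNA | presence of virus |
| Section 3.2, exclusion 6 | HBV, HCV, CMV | DNA | presence of virus |
| Section 5 schedule, footnote 4 | HBV, HCV, CMV | DNA | presence of active virus |
| Section 5.1.1 | HBV, HCV, CMV | DNA | presence of active virus |

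All four are operative text of the current version, not entries in the amendment log.

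2. **Target against genome.** HBV is a DNA virus, so the wording fits. CMV is a DNA virus, so it fits. HCV is an RNA virus, so it does not fit. One of three is wrong, in each of the four places.

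3. **Is DNA just the plan's usual way of writing PCR?** No. For on-treatment CMV surveillance, footnote 5 of the schedule and Section 5.1.1 ask for PCR with no target named. In the reflex test the word DNA is therefore an added specification.

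4. **Does anything else correct it?** Appendix D is confined to hepatitis B serology and gives no HCV assay. No section names an HCV RNA or reverse-transcription test. Section 5.1.2, on central laboratory work, covers correlative samples, cytogenetics and mutations and includes no viral test that would standardize the order.

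5. **What still protects the subject if the wording is followed literally?**
   - Chronic active HCV is an exclusion in its own right, tied to no assay.
   - Ongoing systemic viral infection is a second exclusion, also tied to no assay.
   - Table 1 in Section 6.3.1 tells sites to consider viral infection when liver injury occurs, and to check for viral hepatitis before steroids are started. It names no DNA assay there.

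6. **Does any statistical quantity depend on it?** No. The sample size, the one-sample log-rank test, the endpoint definitions and the analysis populations do not use HCV status.

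**The case against.** The best defense is that this is shorthand which no competent laboratory would take literally. Footnote 4 and Section 5.1.1 say that the purpose is to find active virus. The test is ordered locally, and a laboratory asked for HCV by PCR would most likely run its usual RNA assay. On that view the slip is terminological and has no practical consequence.

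Much of this stands, and it limits the size of the risk. It does not remove the error. A mandatory eligibility test should not depend on each site silently correcting it. The two exclusions that name no assay also need evidence, and in a subject with a positive antibody and no known history the reflex test is where that evidence would come from.

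A reader might go further and infer that the specified test would clear every antibody-positive subject with active HCV, or quote a sensitivity of zero for the trial's screening. The documents do not support this. No section says that a negative PCR makes an antibody-positive subject eligible, although the reflex structure suggests it. No section shows that any laboratory would run a DNA-template assay for HCV.

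A reader might also infer that missed HCV would be recorded as umbralisib liver toxicity. That does not follow either. Table 1 directs sites to look for viral causes, and Section 10.4 requires the investigator to judge the causality of each event.

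**Conclusion.** The text is wrong as written. Exclusion 6, in the synopsis and in Section 3.2, and its repeats in the schedule footnote and Section 5.1.1 name DNA as the PCR target for an RNA virus, and nothing else in the documents puts this right. Followed literally, the required test could not show active HCV.

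The practical risk is small and falls on individual subjects. It would materialize only if an antibody-positive subject with active HCV were screened, the laboratory took the wording literally, and the other exclusions and checks did not pick the infection up. The documents give no HCV prevalence and no screening numbers, so no count of affected subjects among the roughly 55 planned can be derived. The trial's power, error rate and analyses are unaffected.

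The conclusion rests on one fact from outside the documents, that HCV has an RNA genome and HBV and CMV have DNA genomes. It also rests on a judgment that many laboratories would run an RNA assay regardless. If fewer did so, the risk would be larger, but the correction would be the same.

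**What to change.** In exclusion 6 (synopsis and Section 3.2), footnote 4 of the Section 5 schedule and Section 5.1.1, replace the words *by DNA (PCR)* with *by HBV DNA PCR, HCV RNA PCR or CMV DNA PCR, as applicable*.

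In exclusion 6 and Section 5.1.1, make clear that the reference to Appendix D concerns hepatitis B only.

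The cost is a wording change in four places, which can be made with the next amendment. It adds no visit, sample or procedure. Where a site would have ordered the test literally, one laboratory order replaces another, and only for HCV-antibody-positive subjects.

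### Exclusion 10 prints its PSA limit in mg/dL, which equals 10,000 ng/mL, so the PSA condition puts almost no restriction on localized prostate cancer

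*Combined protocol and SAP*

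**What the plan says.** Exclusion 10 in Section 3.2, repeated in the synopsis, starts from a general bar and then lists exceptions: "Malignancy within 3 years of study enrollment except for adequately treated basal, squamous cell carcinoma or non-melanomatous skin cancer". Further exceptions follow, and the last is "localized prostate cancer and PSA <1.0 mg/dL on 2 consecutive measurements at least 3 months apart". A recency rule is then attached to the later of the two values: "with the most recent one being within 4 weeks of study entry".

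A patient using the prostate exception must therefore meet three conditions: the disease is localized, there are two PSA values with the stated spacing and recency, and both lie below the printed limit.

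PSA is mentioned nowhere else. It is absent from the assessment schedule in Section 5 and from the local laboratory list in Section 5.1.1. No section gives a PSA range or a second unit against which the limit could be read.

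Exclusion 9 applies separately and bars "Any severe and/or uncontrolled medical conditions or other conditions that could affect their participation in the study such as" the cardiovascular examples it goes on to list.

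**The concern.** The timing rules ask for two values at least 3 months apart, the later one close to entry. That makes sense if the limit is meant to show that the prostate cancer is under control. A limit printed in mg/dL looks far too high for that purpose and leaves the timing rules with almost nothing to test.

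This is an operative eligibility threshold, not background text. Being localized describes the extent of disease, not its control. The words about adequate treatment stand with the skin cancers at the head of the list and are not clearly carried over to the prostate item. PSA is then the only explicit disease-control condition in this exception.

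Two things are at stake. Patients with localized disease and raised PSA could be admitted although the criterion was probably meant to screen them. And with up to 20 centers (Section 4.3), one site could apply the unit as printed while another silently reads the limit in the unit its laboratory reports, so that eligibility differs by site.

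**Working it through.** **Inputs**
- Limit: below 1.0 mg/dL (exclusion 10, Section 3.2 and synopsis, same unit in both).
- Unit identities: 1 mg = 1,000,000 ng; 1 dL = 100 mL.
- Assumption, not in the documents: laboratories report PSA in ng/mL.

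The limit is a stated value that the plan does not derive, so there is no calculation of the plan's own to reproduce.

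**Conversion**
- 1.0 mg/dL = 1,000,000 ng / 100 mL = 10,000 ng/mL.
- In reverse, 1.0 ng/mL = 100 / 1,000,000 mg/dL = 0.0001 mg/dL.
- If ng/mL had been meant with the same number, the printed limit is 1.0 / 0.0001 = 10,000 times higher.

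**Which values pass**

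| PSA (ng/mL) | PSA (mg/dL) | Below 1.0 mg/dL, as printed | Below 1.0 if the unit were ng/mL |
|---|---|---|---|
| 1 | 0.0001 | passes | fails |
| 4 | 0.0004 | passes | fails |
| 20 | 0.002 | passes | fails |
| 100 | 0.01 | passes | fails |
| 1,000 | 0.1 | passes | fails |
| 9,999 | 0.9999 | passes | fails |
| 10,000 | 1.0 | fails | fails |

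Every value from 1 up to, but not including, 10,000 ng/mL is classified differently under the two readings.

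**What still restricts entry, whatever the unit**
- Prostate cancer that is not localized, within 3 years, does not meet the exception and stays excluded.
- A patient without two consecutive values that meet the spacing and recency rules does not qualify.
- Exclusion 9 still bars severe or uncontrolled conditions, although it rests on judgement and supplies no PSA limit.
- All other malignancies outside the listed exceptions stay excluded.

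The defect is therefore limited to the PSA condition within one exception.

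**The case against.** The strongest reply is that this is a typing slip without demonstrated consequence. The synopsis and Section 3.2 agree with each other, so there is no contradiction to reconcile. If laboratories report in ng/mL, a site may simply compare the reported number with 1.0 and apply the limit as presumably intended. No misapplication is shown, and nothing says how many subjects, if any, entered through this exception. This stands as far as it goes: the practical effect is unknown. It does not remove the defect, because a site that follows the text literally gets almost no screening from it, and no other section states the intended limit.

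A reader might infer more, and the documents do not support it:

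- *That active prostate cancer in general passes exclusion 10, or that the limit can exclude nobody.* The localized condition and the two timed measurements still apply. That no patient reaches 10,000 ng/mL is an outside fact; the documents support only that values at or above it fail.
- *That the primary endpoint is compromised.* PFS counts death from any cause (Section 2.2), so any death without prior progression is an event. Nothing estimates how many subjects would be admitted with raised PSA or would die of prostate cancer during follow-up.
- *That second-malignancy reporting is distorted.* Section 10.8.6 concerns secondary and second primary malignancy events. A cancer known at entry is medical history and becomes an adverse event only if it worsens (Section 10.8.5).
- *That the Phase 1 figures of 73% male and median age 62 show prostate cancer to be the leading competing cancer here.* Section 1.2.2.1 gives those figures for 55 patients with mixed hematologic malignancies, of whom 18 had CLL (18/55 = 33%), and it says nothing about prostate cancer.

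**Conclusion.** The point holds in a limited form. The printed unit sets the PSA limit at 10,000 ng/mL. Among patients with localized prostate cancer who have the two measurements, it gives almost no restriction. The factor of 10,000 describes the gap between the two units, not the harm to the trial. The harm cannot be sized, because the documents do not say how many subjects use the exception or what their PSA values are.

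Calling it a probable unit error rests on one assumption, that PSA is reported in ng/mL; the conversion itself rests on none. Because the same unit is printed in two places, a fault in reading the file is an unlikely explanation.

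The sample size, power, one-sample log-rank test and endpoint definitions are unaffected. This is an eligibility correction worth making, not a threat to the primary analysis.

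**What to change.** The sponsor should confirm the intended PSA unit and limit and correct exclusion 10 in both the synopsis and Section 3.2. This review does not propose a value.

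Subjects already enrolled under the prostate exception should be listed descriptively, with both PSA values, their dates and the unit in which the laboratory reported them. The list would show whether sites applied the criterion in different ways. A subject who met the criterion in force at entry complied with the protocol and should not be recorded as a deviation retroactively.

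The cost is a minor text correction in two places and a short listing check.
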